7.2 Participant discontinuation from the study

Discontinuation from study is when the participant prematurely stops receiving the study treatment infusion, and/or further protocol-required assessments or follow-up, for any reason.

If the participant agrees, a final evaluation at the time of the participant's study discontinuation should be made as detailed in [Section 1.3](#) Schedule of Activities.

7.3 Withdrawal of informed consent and exercise of participants' data privacy rights

Withdrawal of consent/opposition to use of data and/or biological samples occurs in countries where the legal justification to collect and process the data is consent and when a participant:

- Explicitly requests to stop use of their data

and

- No longer wishes to receive study treatment

and

- Does not want any further visits or assessments (including further study-related contacts)

This request should be as per local regulations (e.g., in writing) and recorded in the source documentation.

Withdrawal of consent impacts ability to further contact the participant, collect follow-up data (e.g. to respond to data queries) and potentially other country-specific restrictions. It is therefore very important to ensure accurate recording of withdrawal vs. discontinuation based on the protocol definitions of these terms.

In this situation, the Investigator should make a reasonable effort (e.g., telephone, e-mail, letter) to understand the primary reason for the participant's decision to withdraw their consent/exercise data privacy rights and record this information. The Investigator shall clearly document if the participant has withdrawn his/her consent for the use of data in addition to a study discontinuation.

No further assessments must be conducted, and the data that would have been collected at subsequent visits will be considered missing.

Further attempts to contact the participant are not allowed unless safety findings require communicating or follow-up.

If the participant agrees, a final evaluation at the time of the participant's withdrawal of consent/exercise data privacy rights should be made as detailed in [Section 1.3](#) Schedule of Activities.

Further details on withdrawal of consent or the exercise of participants' data privacy rights are included in the corresponding informed consent form.

7.4 Lost to follow-up

For participants whose status is unclear because they fail to appear for study visits or fail to respond to any site attempts to contact them without stating an intention to discontinue from study treatment or discontinue from study or withdraw consent (or exercise other participants' data privacy rights), the Investigator must show "due diligence" by documenting in the source documents steps taken to contact the participant, e.g., dates of telephone calls, registered letters, etc. A participant should not be considered as lost to follow-up until due diligence has been completed or until the end of the study.

7.5 Study stopping rules

Sponsor will review emergent safety reports on an ongoing basis to react as soon as there is a possibility that a stopping rule could apply. The sponsor will review all SAE as individual cases and will also be able to review summaries of non-serious adverse events for patterns and trends and will first exclude any events determined to be clearly unrelated to study treatments (e.g., SAE which occurred during the pre-treatment screening period, or disease-related SAE expected in the population under study). CCI

CCI

Table 7-1

CCI

CCI

CCI

Table 7-2

CCI

CCI

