6.3.2 Treatment blinding

Participants, Investigator staff (except unblinded pharmacist/unblinded qualified site designee) and persons performing the assessments will remain blinded to the identity of the treatment from the time of randomization until database lock.

Unblinding a single participant at site for safety reasons (necessary for participant management) will occur via an emergency system in place at the site.

Open label supply (TIN816 and placebo) will be provided at sites to the unblinded pharmacist/unblinded qualified site designee in order to prepare study treatment and to conceal treatment code from participants and the Investigators staff performing the assessment.

The following unblinded sponsor roles are required for this study:

- Statistician, programmers or delegates who need to prepare safety reports for the DMC and
- Bioanalysts CCI

Both will receive a copy of the randomization schedule (via request to the Randomization Office), to facilitate analysis of the samples. They will provide the sample data to the study team under blinded conditions unless otherwise allowed. The study statistician will be able to access the randomization list for interim analyses and is allowed to share unblinded information with the rest of the clinical team as appropriate for internal decision purposes, as outlined in [Table 6-2](#). For example, unblinded summaries and unblinded individual data can be shared

with the team for interim analyses. Statistical programmers and other personnel involved in study data analysis (e.g., drug supply manager) are allowed to access treatment assignment information for the purpose of data analysis. The clinical trial team is allowed to share unblinded results with other sponsor staff (e.g., decision boards) as required for internal decision making on the study or the project at the time of IAs while the study is ongoing. All unblinded personnel will otherwise keep randomization lists and data or information that could unblind other study team members confidential and secure except as described above. The DMC will be provided with unblinded results to facilitate the review of safety information (Table 6-2). More details will be provided in the DMC charter about the unblinding plan and data flow. Following final database lock all roles may be considered unblinded. See Table 6-2 for an overview of the blinding/unblinding plan.

Table 6-2 Blinding and unblinding plan

Role	Time or Event			

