8.6.1 Adverse events

An adverse event (AE) is any untoward medical occurrence (e.g., any unfavorable and unintended sign [including abnormal laboratory findings], symptom or disease) in a clinical investigation participant after providing written informed consent for participation in the study. Therefore, an AE may or may not be temporally or causally associated with the use of a medicinal (investigational) product.

The Investigator has the responsibility for managing the safety of individual participants and identifying adverse events.

Novartis qualified medical personnel will be readily available to advise on trial-related medical questions or problems.

The occurrence of adverse events must be sought by non-directive questioning of the participant at each visit during the study. Adverse events also may be detected when they are volunteered by the participant during or between visits or through physical examination findings, laboratory test findings, or other assessments.

Adverse events must be recorded under the signs, symptoms, or diagnosis associated with them, accompanied by the following information (as far as possible) (if the event is serious refer to [Section 8.6.2](#)):

1. CCI (version 5 or higher).

If CCI grading does not exist for an adverse event, use 1=mild; 2=moderate, 3=severe; and 4=life threatening. CCI grade 5 (death) is not used, but is collected in other eCRF (e.g., Study Completion, Death/Survival).

2. Its relationship to the study treatment. If the event is due to lack of efficacy or progression of underlying illness (i.e., progression of the study indication) the assessment of causality will usually be 'Not suspected.' The rationale for this guidance is that the symptoms of a lack of efficacy or progression of underlying illness are not caused by the trial drug, they happen in spite of its administration and/or both lack of efficacy and progression of underlying disease can only be evaluated meaningfully by an analysis of cohorts, not on a single participant
3. Its duration (start and end dates or ongoing) and the outcome must be reported
4. Whether it constitutes a SAE (see [Section 8.6.2](#) for definition of SAE) and which seriousness criteria have been met
5. Action taken regarding with study treatment.

All adverse events must be treated appropriately. Treatment may include one or more of the following:

- Dose not changed
 - Dose Reduced/increased
 - Drug interrupted/permanently discontinued
6. Its outcome

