8.6.3 SAE reporting

To ensure participant safety, every SAE, regardless of causality, occurring after the participant has provided informed consent and until last study visit must be reported to Novartis safety immediately, without undue delay, but under no circumstances later than within 24 hours of obtaining knowledge of the events (Note: If more stringent, local regulations regarding reporting timelines prevail). Detailed instructions regarding the submission process and requirements are to be found in the Investigator folder provided to each site. Information about all SAEs is collected and recorded on the Electronic Serious Adverse Event (eSAE) or Serious Adverse Event Report Form; all applicable sections of the form must be completed in order to provide a clinically thorough report. SAEs occurring after the participant has provided informed consent until the time the participant is deemed a Screen Failure must be reported to Novartis.

Event common in the participant population under study: Investigators will report AEs or SAEs that are commonly seen in the study population, but they will not be unblinded and will not be reported as Suspected Unexpected Serious Adverse Reaction (SUSAR) to regulatory agencies, ECs, or investigators during the study. In clinical trials evaluating treatments for high morbidity and/or high mortality disease states, SAEs that are known consequences of the underlying disease or condition under investigation, or events common in the study population, are anticipated to occur with some frequency during the course of the study, regardless of drug exposure. While the investigator must still report all SAEs, SUSARS considered consistent with the following SAE Preferred Terms (PT) will not be unblinded and reported in an expedited timeframe to regulatory agencies, ECs or investigators during the course of the study. These events will be presented in the clinical study report at the end of the study: acute kidney injury (PT)

If specifically requested by a local Health Authority (HA), pre-specified SAEs that also meet the criteria for SUSARs will be expedited to this HA as blinded reports. Investigator Notification (IN) will not be issued for these events.

OR

Pre-specified SAEs commonly observed in the study population that occur in patients under the jurisdiction of the requesting Health Authority will be expedited to the Health Authority as unblinded reports; INs will be issued for these events.

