8.6.5 Disease-related events and/or disease-related outcomes not qualifying as AEs or SAEs

Not applicable.

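### Section 7.5 allows expected disease-related SAEs to be set aside case by case before the stopping rules apply, although section 8.6.1 says disease progression cannot be judged on single cases

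*Protocol*

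**What the plan says.** Section 7.5 (Study stopping rules) describes an ongoing sponsor review intended to react promptly when a stopping rule might apply. "The sponsor will review all SAE as individual cases"; the mention of patterns and trends in the same sentence attaches to summaries of non-serious events. The sponsor "will first exclude any events determined to be clearly unrelated to study treatments". Two examples follow: SAEs from the pre-treatment screening period, and "disease-related SAE expected in the population under study". The criteria themselves (Tables 7-1 and 7-2 and the text around them) are redacted.

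Section 8.6.1 (Adverse events) advises that events due to lack of efficacy or to progression of the study indication will usually be rated as not suspected. Part of its reason is that "both lack of efficacy and progression of underlying disease can only be evaluated meaningfully by an analysis of cohorts, not on a single participant".

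Section 8.6.3 (SAE reporting) names one preferred term, acute kidney injury, as common in this population. SUSARs with that term are not unblinded or expedited during the study, apart from health-authority requests. Section 8.6.5, headed "Disease-related events and/or disease-related outcomes not qualifying as AEs or SAEs", is marked not applicable.

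On other safeguards, section 6.3.2 states: "The DMC will be provided with unblinded results to facilitate the review of safety information". Section 10.1.4.1 lets the DMC recommend termination, and section 7.6 lets the sponsor terminate for an unacceptable safety risk.

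**The concern.** The two examples in 7.5 differ in kind. An SAE that began before treatment is unrelated by timing. An SAE that is merely expected in the population is not: expectedness is a statement about the background rate, whereas relatedness is a statement about cause.

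A stopping rule exists to detect an excess over background. If events of the background type are removed one at a time because they belong to the background, any excess of the same type goes with them, and no single removal looks wrong. AKI is the most exposed event. It is the study indication, it is the only event that 8.6.3 names as common, and a harmful renal effect of TIN816 would look clinically like the AKI that surgery causes. This is the first trial of TIN816 in patients, so there is little earlier patient experience on which to base a single-case judgement.

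**Working it through.** **Comparison of the texts.** The plan shows no figure to reproduce here, because the stopping thresholds and the sample-size section are redacted. The finding rests on the wording.

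| Question | 7.5 | 8.6.1 | 8.6.3 | 8.6.5 |
|---|---|---|---|---|
| Level at which SAEs are judged | Individual case | Disease progression: cohort only | – | – |
| Which events count as expected | No list or criterion visible | – | AKI only, for SUSAR handling | No list (not applicable) |
| By-arm comparison of set-aside SAEs | None visible | – | – | – |

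Section 7.5 asks for a single-case decision of the kind that 8.6.1 says cannot be made meaningfully. No redacted text is needed to see that conflict, although redacted text could qualify how it works in practice.

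**Illustration of scale.** These are not document figures.

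Inputs from the protocol: about 120 participants (1.1); AKI in up to 15–40% of adults after bypass surgery, depending on the definition (2.2); one-sided tests at 0.1 (9.2.1).

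Assumptions: allocation of TIN816 to placebo 60:60 or 80:40 (the ratio is redacted); the two dose groups taken together for simplicity; relative risk (RR) on TIN816 of 1.5 or 2.0; every AKI case an SAE; the 0.1 level applied to a comparison for harm with all participants in.

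Formulas, with p0 the placebo risk, p1 = p0 × RR, n0 and nT the arm sizes, and p̄ the pooled risk:

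- Expected excess = nT × (p1 − p0)
- Power = Φ{[(p1 − p0) − 1.2816 × √(p̄(1−p̄)(1/n0 + 1/nT))] / √(p0(1−p0)/n0 + p1(1−p1)/nT)}

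Worked row (60:60, p0 = 0.15, RR = 1.5):

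- p1 = 0.225, so the excess is 60 × 0.075 = 4.5.
- p̄ = 0.1875, and the two standard errors are 0.0713 and 0.0709.
- Power = Φ{(0.075 − 1.2816 × 0.0713)/0.0709} = 0.41.

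| p0 | RR | p1 | Excess, 60:60 | Power, 60:60 | Excess, 80:40 | Power, 80:40 |
|---|---|---|---|---|---|---|
| 0.15 | 1.5 | 0.225 | 4.5 | 0.41 | 6 | 0.37 |
| 0.15 | 2.0 | 0.300 | 9 | 0.76 | 12 | 0.71 |
| 0.275 | 1.5 | 0.4125 | 8.25 | 0.62 | 11 | 0.58 |
| 0.275 | 2.0 | 0.550 | 16.5 | 0.97 | 22 | 0.95 |
| 0.40 | 1.5 | 0.600 | 12 | 0.82 | 16 | 0.79 |
| 0.40 | 2.0 | 0.800 | 24 | >0.99 | 32 | >0.99 |

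If every AKI SAE were set aside as expected, the number reaching the stopping review would be 0 in every row. A by-arm count of the same events would have between 37% and more than 99% power to show the excess.

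The table overstates what an actual look would achieve. The 15–40% covers AKI of any severity, not SAEs. Section 9.2.1 keeps the dose groups separate, and a DMC meeting during the trial would have fewer participants. The contrast between the two ways of looking does not depend on the exact numbers.

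**The case against.** Much of the opposing case stands.

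- **The exclusion is a judgement.** It covers events that have been determined to be unrelated, and expected disease-related SAEs are an example of what may be so determined. A reader might infer that an excess of AKI would never be counted. The text supports only that it could be left out.
- **The criteria are redacted.** They may name AKI, bleeding or death, or set out an adjudication or by-arm step. What is blacked out cannot be treated as missing from the plan.
- **Bleeding and death are not classed as expected.** A reader might extend the point to them, since both occur after bypass surgery. No visible text calls either an expected disease-related SAE. Bleeding is handled as a monitored risk: active bleeding bars dosing (5.2), and bleeding and coagulation parameters are followed (8.4.7).
- **Section 8.6.3 is not a second filter on the stopping count.** A reader might add the not-suspected guidance, the SUSAR provision and 7.5 together as successive removals of AKI. The SUSAR provision governs unblinding and expedited reporting. A SUSAR is by definition suspected, so it should not be clearly unrelated under 7.5. Section 8.6.3 also requires every SAE to reach the sponsor within 24 hours, whatever its causality.
- **Other routes to stopping exist.** The DMC reviews unblinded safety data and can recommend termination. SAP section 1 confirms that analyses were prepared for DMC meetings during the study. Sections 7.6 and 4.6 allow termination or an extra interim analysis on safety grounds.

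These points limit the conclusion without removing the conflict. The DMC meets at intervals and 7.6 is discretionary, whereas 7.5 is the continuous trigger. Nothing visible says that the SAEs set aside under 7.5 are brought together by arm for anyone.

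**Conclusion.** The point holds in limited form. Section 7.5 presents expectedness as an example of clear unrelatedness and applies it case by case, while 8.6.1 says that such events can be evaluated only across cohorts. A drug-related excess of AKI could therefore drop out of the ongoing stopping review. On the assumptions shown, that excess would be 4.5 to 32 cases among 120 participants, with none counted in the extreme case that all are set aside. The size depends wholly on the assumed allocation, relative risk and seriousness of AKI.

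The documents do not show that an excess would go undetected, that bleeding or death is affected, or that the redacted criteria share the fault. The unblinded DMC and section 7.6 remain as backstops. Reporting at the end of the study is not in question, since SAP section 2.7.1 summarises SAEs by treatment group.

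**What to change.** - **Reconcile 7.5 with 8.6.1.** State that expectedness alone does not make an SAE starting after the infusion clearly unrelated. Pre-treatment SAEs may still be excluded by timing. State which events may be set aside as disease-related and by what criterion, and make clear that the AKI listing in 8.6.3 concerns SUSAR handling only.
- **Add a by-arm check.** Tabulate every post-infusion SAE set aside as disease-related, cumulatively by arm and against concurrent placebo, in the existing unblinded DMC package.
- **Check the thresholds before changing what counts.** The redacted thresholds may have been set on the understanding that background events are removed. If so, counting all AKI against them could trigger them without a drug effect (15–40% of 120 is 18 to 48 cases from background alone). The sponsor should establish this first.

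The cost is a short rewording of 7.5, one further DMC table, and possibly more alerts for the sponsor and DMC to review.

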7.6 Early study termination by the Sponsor

The study can be terminated by Novartis at any time.

Reasons for early termination (but not limited to):

- Unexpected, significant, or unacceptable safety risk to participants enrolled in the study
- Decision based on recommendations from applicable board(s) after review of safety and efficacy data
- Discontinuation of study treatment development in this indication

In taking the decision to terminate, Novartis will always consider participant welfare and safety. Should early termination be necessary, participants must be seen as soon as possible and treated as a participant who discontinued from the study: the participant should come for a final End of Study (EOS) visit. The Investigator may be informed of additional procedures to be followed in order to ensure that adequate consideration is given to the protection of the participant's interests. The Investigator or Novartis depending on local regulation will be responsible for informing IRBs/IECs of the early termination of the trial.

8 Study Assessments and Procedures

Study procedures and their timing are summarized in [Section 1.3](#) Schedule of Activities. Protocol waivers or exemptions are not allowed.

- Immediate safety concerns should be discussed with Novartis upon occurrence or awareness to determine if the participant should continue or discontinue study treatment.
- Adherence to the study design requirements, including those specified in [Section 1.3](#) Schedule of Activities, is essential and required for study conduct.
- Safety/laboratory/analyte results that could unblind the study will not be reported to investigative sites or other blinded personnel until the study has been unblinded.
- Repeat or unscheduled samples may be taken for safety reasons or for technical issues with the samples.

8.1 Screening

Procedures conducted as part of the participant's routine clinical management/standard of care (e.g., clinical chemistry, hematology, urinalysis) and obtained before signing of the ICF may be utilized for screening or baseline purposes provided the procedures met the

protocol-specified criteria and were performed within the timeframe defined in [Section 1.3](#) Schedule of Activities.

8.1.1 Eligibility screening

Results of below screening evaluation will be available as source data at the study site and will not be recorded within the eCRF.

8.1.1.1 Hepatitis screen, HIV screen, Tuberculosis screen

All participants will be evaluated for active hepatitis (refer to exclusion criterion 28).

Evaluation of history of immunodeficiency diseases or known positive HIV test documented in source data. Notification of state and federal authorities, as required by law, will be the responsibility of the Investigator.

Determination of TB status will be required before administration of study treatment and should be performed as defined by local guidelines (refer to exclusion criterion 29).

8.1.1.2 Alcohol test, drug screen

Participants will be assessed by the Investigator at screening for history of drug abuse and unhealthy alcohol use as described in Exclusion criterion 30. A positive evaluation will lead to the exclusion of the participant.

8.1.2 Information to be collected on screening failures

Participants who sign an informed consent form and are subsequently found to be ineligible (either pre-surgery, or during or shortly after surgery but prior to IMP infusion) will be considered a screen failure.

The reason for screen failure should be entered on the applicable Case Report Form. The demographic information, informed consent, and Inclusion/Exclusion pages must also be completed for screen failure participants. No other data will be entered into the clinical database for participants who are screen failures, unless the participant experienced a serious adverse event during the screening phase (see [Section 8.6](#) Serious adverse events for reporting details).

Participants who sign an informed consent and are considered eligible but fail to be started on treatment for any reason will be considered an early terminator. The reason for early termination should be captured on the appropriate disposition Case Report Form.

